# 2. **Objectives**

There are two primary objectives and seven secondary objectives for this proposal. Primary objectives (i.e., Specific Aims #1 and #2) are:

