# Specific Aim #1: To test the effectiveness of ketamine augmentation to usual care (fentanyl) (K+UC) relative to Usual Care (UC) in reducing the severity of acute nociceptive pain in response to pressure at: a) the burn wound (primary hyperalgesia); b) in body areas adjacent to the burn (secondary hyperalgesia) and; c) body areas distal to the burn (allodynia).

The standard of care for wound care procedures among adults with acute intermediate and/or deep burns involves twice daily wound care procedures. Each wound care procedure, especially during the first week, involves moderate to severe pain during dressing removal, debridement, wound cleansing, reapplication of topical ointment, and dressing replacement.

To compare and contrast the K+UC condition relative to the UC condition for reducing acute nociceptive pain, we will measure the following: 1) Self-reported pain and pain unpleasantness; 2) Sympathetic arousal; 3) Time until maximal pain relief; 4) Post-procedure, self-rated recall of average pain and pain unpleasantness following each wound care procedure, and self-rated satisfaction with pain management. Each of these is described below.

1) **Self-reported pain:** Pain is operationally defined as participant self-reported pain severity at the time of assessment, using the Numeric Analogue Scale (NAS) (McCaffrey, Pasero, 1999). NAS

Assessments will be performed within 5 minutes prior to administration of K+UC or UC, at the onset of the wound care procedure, every 10 minutes during each procedure, and at 15, 30, 45 and 60 minutes after the first and second procedures of the day, and, again at 6-hours post-procedure for the 1st wound care session each day.

The protocol standardizes body surface areas (wound, proximal, distal) where pain will be measured in the context of standardized pressure, and the duration and interval before releasing pressure. That is, pressure will be applied to each area, in turn, using standard force and a single fingertip, as when assessing skin blanching. This will be repeated once at each body location (wound, proximal, distal) assessed at the 30 minutes and 1-hour assessments during the first sessions on Day 1 (Session 1), Day 3 (Session 1), Day 5 (Session 1) and Day 7 (Session 1) and again at 1 hour after each of these wound care sessions is completed.

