**Central Sensitization** - The NAS will be rated in regards to each of the following 3 patientspecific areas at each specified time point: a) Within the wound area (primary hyperalgesia); b) Skin proximal to but outside the wound area (secondary hyperalgesia) and c) Generalized pain at skin distal from the wound (allodynia). The repeated assessment of pain severity during the wound care will allow for evaluating increased pain hypersensitivity (hyperalgesia), and the assessment of pain for 1 hour afterwards will enable us to detect enhanced temporal summation of pain as has been observed among combat veterans with PTSD relative to combat veterans without PTSD and non-service members without PTSD (see below, Moeller-Bertram, Strigo, et al., 2016)

2) **Sympathetic arousal:** This will be measured using an Itamar Watch-PAT 200. This is a device that will be worn by all subjects while in the burn unit. In addition to providing measures of sympathetic reactivity prior to, during and after wound care, this device will also provide measures of sleep. A description of this device is provided at: https://www.youtube.com/watch?v=wE4pVhvS5Xg

3) Time to maximal pain relief and duration of time at maximal pain relief: These are operationally defined as: time elapsed between the start of wound care and the time at which the lowest pain rating is reported by each participant for each wound care session, and, the number of 10-minute observations where pain is reported at that maximal relief pain score. Thus, the NAS ratings will be used to create change scores (each NAS score subtracted from baseline score) with the largest change from baseline score designated as maximal pain relief. If the maximal pain relief is reflected in more than one rating, the first of these will represent the time to maximal pain relief.

4) **Recall Effect on Pain and Satisfaction With Pain Management:** This is defined as patient recall of average pain, and rating of satisfaction with wound care pain management. Recall of the average pain experienced during each of the 14 procedures will be rated 1-hour after each wound care sessions ends, and 6 hours afterward each AM session ends measured with the same 0-10 point NAS used to rate pain during the wound care procedure. This will allow testing of the well-documented memory effect whereby the worst and the last pain ratings during the procedure will best predict memory for pain afterwards.

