## Specific Aim #2: To determine whether adjunctive ketamine is associated with opiate sparing.

This will be measured by documenting each participant's number of Requests for Additional Analgesic Medications (i.e., RAAMs) for acute nociceptive pain during each of the 14 wound care procedures from Day 1 to Day 7 of the Trial.

**The seven secondary outcome measures** of the proposal are: 1) Rates of acute and posttraumatic stress disorder (i.e., ASD and PTSD); 2) Rates of major depressive disorder; 3) Sleep quality and duration; 4) Pain-related anxiety; 5) Catastrophizing; 6) Emotion Regulation and; 7) Trauma resilience.

1) ASD and PTSD will be assessed using the Diagnostic and Statistical Manual of Mental Disorders V-(DSM V). By definition, to meet criteria for PTSD, symptoms must be present for 1 month. As such, prior to the 1-month post-injury time-point, subjects with symptoms consistent with PTSD related to their burn injury will be diagnosed with ASD, rather than PTSD. It is hypothesized that subjects in the K + UC group will have a lower percentage of patients who meet criteria for PTSD, when compared to subjects in the UC group. It is also hypothesized that a number of factors will moderate the presence and severity of ASD and PTSD; these include:

a) Pain, as measured above. Mutual Maintenance Theory: We anticipate that "mean pain" of all 14 sessions (i.e., group average of all observations across all 14 sessions) and the trajectory of pain through the 14 sessions (i.e., group X individual trajectory within session, and, group X individual trajectory across all 14 sessions) will be predictive of PTSD development and PTSD symptom severity at 1-month.

b) Sympathetic reactivity (as measured above). We expect that greater sympathetic reactivity during the wound care procedures will be associated with ASD and PTSD.

c) Depressive symptom severity as measured using the Beck Depression Inventory (BDI-II) during the week of wound care, and at the 1-month time-point.

d) Sleep during the night following wound procedures (measured by both self-report and with the Itamar Watch-PAT200) and at the 1-month time point (self-report).

e) Trauma Resilience (as measured using the Trauma Resilience Scale: Trait- at baseline, and at 1-month time-point).

f) Distress at baseline in reporting the burn event (as measured by self-report and the Itamar Watch-PAT200)

g) Optimism (as measured by the Life Orientation Test: Trait – baseline)

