#### 1. Sample Size Estimate Based on Stay $\geq$ 7 days in Burn ICU.

The sample size calculation is based on the primary statistical procedure for this project which will test the difference in mean pain scores, defined as the average self-report of mean pain score, based on the Numeric Analogue Scale (NAS), during each burn wound care procedures, between individuals randomized to usual care plus placebo (fentanyl plus saline) and those randomized to the intervention arm (usual care + ketamine). PASS Sample Size (Version 14) was used to perform all sample size calculations while considering individuals over the one-year study duration randomized to control and intervention arms in a 1:1 fashion.

In the first case, we further assume that each individual, will, on average, have a length of stay of 7 days thus resulting in 14 wound care procedures performed during hospital stay. We determined the minimum sample size for our trial based on 80% power at p = 0.05 to detect a clinically significant difference in mean pain score during the wound care procedure of 2.0 points between the control and intervention arms with a standard deviation of 3.0. In addition, to account for the clustered nature of procedures performed on individuals, we have used a sample size inflator (also termed "design effect") of 10.1 as described by the Cochrane manual@ conservatively using an interclass correlation of effects of 0.7 amongst repeated measures of pain scores within each individual and 14 observations per individual.

The required sample size needed to accept the alternative hypotheses that the mean pain care score in the intervention arm decreased by 2 points compared to the control arm at the 0.05 level would require 27 individuals per arm (54 total), our anticipated population of 74 eligible individuals is adequate to show a clinically significant improvement for both intervention arms.

@http://handbook.cochrane.org/chapter\_16/16\_3\_4\_approximate\_analyses\_of\_cluster\_randomized\_trials\_for\_a.htm

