# Data Analysis Plan

[name], a professional biostatistician from the JH BEAD program specializing in clinical trials and longitudinal data analysis, had assisted Drs. [name] and [name] in conducting the statistical analyses in consultation with Going forward, this role will be assumed by biostatisticians at the JHU-ICTR.

The primary data analyses (Pain variables) will be conducted using analysis of covariance, or, longitudinal growth modeling (if normality assumptions are met) to examine group differences both in cross-section and longitudinally. If normality assumptions are violated then appropriate nonparametric tests will be utilized (e.g., Wald statistic). These methods allow for statistical controlling multiple potential confounding baseline variables and are robust against dropout - expected to be minimal. Data from the following study were used to generate this power estimate (Beaudoin, 2014).

Prior to study start-up, it is anticipated that, since ANCOVA is the recommended procedure for analyzing pre- to post- treatment change scores, that is the test that will be utilized for the primary aim, because: it is more powerful than t-test and Mann-Whitney; it can adjust for baseline group differences; it can be adjusted for baseline randomization strata; and, it can be utilized in analyzing repeated measures such as in the present study.

Prior to testing hypotheses, univariate distributions of variables will be inspected to assess normality, identify outliers, skewness or other abnormalities in distribution, determine appropriate summaries of location and spread and the need for transformation or nonparametric analysis. Preliminary analyses will determine whether the data meet basic assumptions for parametric tests. If relevant covariates are not balanced by the randomization, or confounds are distributed unevenly across groups, they will be included in the models as covariates.

If Pain Intensity is substantially associated with non-study factors (e.g., age, gender, TBSA) these variables will be statistically controlled as indicated in analyses.

The data on average (or summed) Opiate Sparing Effects from baseline to post-treatment, and within group and between group changes over time are likely not to meet criteria for parametric analysis, that is, they are expected to be non-normally distributed and thus inappropriate for Analysis of Covariance (ANCOVA).

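### The sample size powers one endpoint (mean NAS during wound care), but Aim 1, the Data Analysis Plan and the dropout rule describe others, and the two primary aims have no testing order

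*Combined protocol and SAP*

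**What the plan says.** **Objectives.** Section 2 states: "There are two primary objectives and seven secondary objectives for this proposal". Aim 1 compares the arms "in reducing the severity of acute nociceptive pain in response to pressure at" the wound, adjacent skin and distal skin. It then lists four families of measures without ranking them. NAS is taken before dosing, "at the onset of the wound care procedure, every 10 minutes during each procedure", and afterwards. Pressure is applied at the 30-minute and 1-hour assessments "during the first sessions on Day 1 (Session 1), Day 3 (Session 1), Day 5 (Session 1) and Day 7", and again 1 hour after those sessions. Under Central Sensitization: "The NAS will be rated in regards to each of the following 3 patientspecific areas at each specified time point". Aim 2, also primary, is "To determine whether adjunctive ketamine is associated with opiate sparing", counted as requests for additional analgesia.

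**Sample size.** Both estimates rest on "the primary statistical procedure for this project which will test the difference in mean pain scores" during wound care. The corrected estimate uses a difference of 2.0, SD 4.0, intraclass correlation 0.7 and 11 sessions, and gives 47 per arm.

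**Section 7.** The primary outcome is given only by pointing back to earlier text. The Data Analysis Plan allows ANCOVA or longitudinal growth modeling, with nonparametric tests if normality fails. It anticipates ANCOVA for "analyzing pre- to post- treatment change scores, that is the test that will be utilized for the primary aim". Covariates enter if randomization leaves them unbalanced or if they are substantially associated with the outcome. The Randomization text in section 4 adds a similar if-necessary rule. The opiate-sparing paragraph repeats these rules and names Mann-Whitney or another nonparametric method. Under Participant Dropout, the last data obtained become the endpoint for patients who leave early.

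**The concern.** Four parts of the plan describe four different quantities: a mean over sessions (sample size), pressure-evoked pain at three sites (Aim 1), something justified by pre-to-post change (Data Analysis Plan), and possibly a last value (Participant Dropout). The stated 80% power belongs only to the first.

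Both aims are primary, and no text says whether success on one is enough, whether both are needed, or which is tested first. The rules for model, test and covariates depend on the observed data and carry no cut-offs. Two competent analysts could therefore report different primary results from the same data set, and a positive claim could rest on choices made after the data were seen.

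**Working it through.** **1. Reproduce the plan's figures** (two-sided 0.05, 80% power, two-sample t-test; sidedness is not stated, but two-sided reproduces).
- Design effect = 1 + (m − 1) × 0.7: m = 11 gives 8.0; m = 14 gives 10.1.
- Corrected estimate: difference 2, SD 4.0 needs 64 per arm with one observation each; 64 × 8.0/11 = 46.5, so 47. This matches.
- Seven-day estimate: SD 3.0 needs 37; 37 × 10.1/14 = 26.7, so 27. This matches.

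Both results are tests of a session average.

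**2. Power by number of sessions averaged.** SD of a patient mean = 4 × √[(1 + (k − 1) × 0.7)/k], with 47 per arm and difference 2.

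| Sessions k | SD | Power |
|---|---|---|
| 11 | 3.411 | 80.3% |
| 4 | 3.521 | 77.8% |
| 3 | 3.578 | 76.5% |
| 1 | 4.000 | 67% |

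Pressure testing falls in 4 sessions over seven days, or 3 (days 1, 3 and 5) in a 5.5-day stay. Assuming the same SD, correlation and difference, that endpoint has 76-78% power.

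**3. Dropout rule read as a last value for early leavers only.** Let p be the assumed share leaving early. Variance = (1 − p) × 3.411² + p × 4.0².
- p = 20%: 12.51, power 77%.
- p = 60%: 14.26, power 72%.

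If leavers contribute the mean of their observed sessions instead:
- 6 sessions each: 80.1% (p = 20%) and 79.6% (p = 60%).
- 3 sessions each: 79.5% and 78.0%.

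A 500-run simulation of a random-intercept model without covariates, with an assumed 42% leaving after 6 sessions, gave 79.6% power and 4.6% type I error.

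**4. Two primary tests, each at 0.05, if either success counts.** Independent: 1 − 0.95² = 9.75%. With correlated normal statistics: 9.1% at 0.5, 8.4% at 0.7 and 7.0% at 0.9. A fixed order keeps 5%.

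**5. Data-driven rules applied literally.** With assumed cut-offs (normality p < 0.05, imbalance p < 0.10, association p < 0.05), N = 94 and 6,000 simulated trials, type I error was 5.0%, 4.7% and 5.1% when three covariates each correlated 0.1, 0.2 and 0.3 with outcome.

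**The case against.** The sample-size section does name a primary comparison, and by confining it to pain during the procedure it already excludes pre-dose and post-procedure ratings. What stays open is narrower: the body site, and whether the onset rating counts.

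Pain is also given implied priority. The sample-size section calls its test the primary procedure, the Data Analysis Plan ties its primary analyses to pain variables, and the ANCOVA sentence speaks of a single primary aim. That is a fair reading of intent, but it is not a testing order, because section 2 makes Aim 2 primary too.

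The ANCOVA sentence gives change scores as a reason for the method and adds that ANCOVA can handle repeated measures. It does not firmly commit to a single change score. A reader might infer that power drops to the 67% of one value per patient; the text does not say that one value is used, and baseline adjustment could raise that figure.

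The database paragraph in section 4 expects multilevel analysis of the 14 repeated measures. That favours the milder reading of the dropout rule, in which follow-up simply ends at the last data.

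Three other stronger readings also fail:
- **A 9.75% error rate as fact.** This needs an either-aim success rule, which is not stated, and independent tests, which is unlikely because NAS triggers the offer of PRN fentanyl.
- **Covariate rules that inflate error by themselves.** With fixed cut-offs they give about 5%; the problem is the freedom to choose.
- **The admissions table showing 42% early leavers** (128 − 74 = 54; 54/128 = 42%). Those patients stayed at least 5.5 days, or about 11 sessions, which the 94 already assumes.

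**Conclusion.** The mismatch stands on the text, and the plan should be corrected before unblinding. The planned N is arithmetically sound for the session mean. Aim 1's wording, section 7 and possibly the dropout rule refer to something else, and no order governs the two primary aims.

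The numerical effects are modest and conditional:
- At most 9.75% false-claim risk, less with correlated aims, and only if either aim suffices.
- A loss of about 3 to 8 points of power, only if the dropout rule means a last value and 20% to 60% leave early (assumed shares).
- A loss of about 2 to 4 points if pressure-evoked pain were the endpoint, under the same SD, correlation and difference.

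The main issue is unconstrained choice after the data are seen. Confidence is moderate, because several parts depend on how ambiguous sentences are read.

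**What to change.** 1. **Endpoint.** In Aim 1 and section 7, name mean NAS during wound care as the single primary endpoint, built from the routine onset and 10-minute ratings. First reconcile the Aim 1 schedule with the Central Sensitization text: the three-site ratings may be only the pressure ratings, and it is unclear whether a non-pressure rating is also taken when pressure is applied at 30 minutes and 1 hour. Make pressure-site pain and the other Aim 1 measures secondary.
2. **Model.** Pre-state one mixed model on all observed sessions: arm, session number, first NAS before session 1 (listed under Randomization), a short fixed covariate list and a random patient intercept. Age, gender and TBSA would serve; the plan gives them only as examples. Delete the normality, imbalance and association rules for this test, and keep a rank test as sensitivity analysis.
3. **Dropout.** State that the last-data rule does not apply to this test.
4. **Order.** Test Aim 2 at 0.05 only if Aim 1 is significant, with one named test, for example Mann-Whitney on requests per session attended.

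**Cost.** An IRB Change in Research, no new data, and no confirmatory claim for Aim 2 if Aim 1 fails. By an ANCOVA approximation, four baseline covariates cost about 2 points of power if they explain nothing (78%) and break even at about 5% of variance explained (81%); the documents give no such correlation. The alternative, an equal alpha split, would cut Aim 1 power to 71%, 74% or 76% at 94, 100 or 104 patients, from 80%, 83% and 84%.

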Group assignment will be based on serial admissions meeting study inclusion / exclusion criteria. Randomization as described above is expected to achieve group equivalence in: 1) the first pain severity score obtained using the Numeric Analogue Scale measured during the1st exam prior to the first wound care session in the Burn Center; 2) the TBSA; 3) the need for surgery; 4) the average length of wound care procedures and; 5) "other" variables, including the distribution of baseline symptom severity of acute stress disorder, depression, anxiety, and insomnia (which will all be assessed at study enrollment before the first target dressing change). Baseline data on participants will be recorded, and comparability between study groups will be examined at 25% (n=  $\sim$ 19-24/group) and 50% (n=  $\sim$ 37-47/group) of study completion to assess presence of balancing issues. These same data will also be examined upon study completion (n= 74-94), and their relationship with core outcome targets will be examined. If necessary, their effect will be taken into consideration in planned analyses.

It is anticipated that, given the large sample size, the process of random assignment will ensure adequate balancing across study conditions (Usual Care Condition, Usual Care PLUS Ketamine Augmentation Condition) of potentially confounding variables. That is, for example, participants differing by clinically important variables such as smaller versus larger burns should be equally represented in both groups. The large sample size and the process of random assignment are deemed more than adequate to ensure representation across the two study arms for the differences in important but extraneous variables such as procedure duration and other aspects of wound care, rehabilitation and surgery.

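### The covariates of the primary pain model are chosen from the trial data and its baseline is undefined; the pre-first-dose NAS and TBSA should be fixed in advance

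*Combined protocol and SAP*

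**What the plan says.** Three rules govern covariates, and all depend on the accumulated data.

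- **Imbalance rule** (section 7, Data Analysis Plan): "If relevant covariates are not balanced by the randomization, or confounds are distributed unevenly across groups, they will be included in the models".
- **Association rule** (same section): "If Pain Intensity is substantially associated with non-study factors (e.g., age, gender, TBSA) these variables will be statistically controlled as indicated in analyses".
- **Review at study completion** (section 4, text following Randomization). Baseline variables, including the first NAS and TBSA, are compared between arms, and "their relationship with core outcome targets will be examined. If necessary, their effect will be taken into consideration in planned analyses".

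No section lists the covariates, says how imbalance is judged, or says how strong an association must be.

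The Data Analysis Plan also names a test for the primary aim: "since ANCOVA is the recommended procedure for analyzing pre- to post- treatment change scores, that is the test that will be utilized for the primary". Among its reasons are that ANCOVA has more power than a t-test and is able to adjust for baseline differences. That describes what the method can do; it does not name a model term.

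No baseline is specified for those change scores. The only definition of a change score is in Specific Aim #1, under time to maximal pain relief: "the NAS ratings will be used to create change scores (each NAS score subtracted from baseline score"). It does not say which baseline. The NAS schedule in the same Aim places a rating in the five minutes before study drug. The randomization text adds a NAS at the first examination, before the first session.

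**The concern.** A confirmatory analysis should be reproducible from the plan by someone who has not seen the outcomes. Here two competent analysts could fit different primary models and both be following the plan. That leaves room, intended or not, for the model to follow the result.

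The imbalance rule also rests on a poor criterion. Randomization makes the unadjusted comparison valid whatever the chance imbalance. The reason to adjust is that a baseline value predicts the outcome, and that reason is just as strong when the arms happen to match.

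The open baseline raises a separate issue. If baseline were taken as each session's pre-dose rating, every such rating from session 2 onward would be post-randomization. The trial hypothesizes reduced hyperalgesia, so those ratings could already carry part of the treatment effect, and subtracting or adjusting for them would remove it.

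**Working it through.** **Inputs from the documents** (section 4, corrected sample size estimate): difference 2.0 points, SD 4.0, intraclass correlation 0.7, 11 sessions per person, alpha 0.05 (taken as two-sided), 80% power, 1:1 allocation. Section 7 treats 74 participants (37 per arm) as sufficient if funding ends early.

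**Inputs assumed** (the documents give none): correlation of baseline NAS with a patient's mean pain, 0.3 to 0.7; of TBSA with mean pain, 0.2; carryover onto the next pre-dose rating, 0.5 or 1.0 point.

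**1. The plan's sample size reproduces.** The design effect is 1 + (11 − 1) × 0.7 = 8.0. A two-sample t-test for 2.0 points with SD 4 needs 64 per arm. Then 64 × 8.0 / 11 = 46.5, so 47 per arm, as stated. Equivalently, the SD of a patient's mean is 4 × √(8.0/11) = 3.41.

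**2. Fixed adjustment against no adjustment.** A baseline with correlation r multiplies the residual SD by √(1 − r²). For r = 0.5, 3.41 × √0.75 = 2.95.

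| r (assumed) | Power, 47 per arm | Power, 37 per arm |
|---|---|---|
| 0 (unadjusted) | 80.3% | 70.1% |
| 0.3 | 83.8% | 74.2% |
| 0.5 | 90.1% | 81.9% |
| 0.6 | 94.0% | 87.5% |

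**3. Fixed adjustment against the plan's rules.** Simulation at 47 per arm with NAS and TBSA prognostic and two further covariates null; 4,000 runs under the 2.0-point effect and 8,000 under no effect. The plan has no cut-offs, so cut-offs for both triggers had to be assumed.

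| Rule | Power at NAS r = 0.3 / 0.5 / 0.7 | Type I error |
|---|---|---|
| Unadjusted | 0.80 / 0.81 / 0.80 | 0.047 / 0.053 / 0.051 |
| Imbalance rule only | 0.81 / 0.81 / 0.82 | 0.046 / 0.045 / 0.037 |
| Both rules together | 0.84 / 0.91 / 0.98 | 0.050 / 0.048 / 0.045 |
| Fixed NAS and TBSA | 0.85 / 0.91 / 0.98 | 0.048 / 0.047 / 0.046 |

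The imbalance rule alone recovers almost none of the available precision. The two rules together recover nearly all of it: before rounding, fixed adjustment leads by 0.9, 0.6 and 0.6 points. A second simulation put the lead at 1 to 2 points, so 0 to 2 is a fair range. Bias was at most 0.012 SD, or 0.012 × 3.41 = 0.04 NAS points.

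**4. What discretion could do.** Simulation with no treatment effect, 47 per arm, 8,000 runs, NAS r = 0.3 to 0.7:

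- fixed NAS plus TBSA: 4.6% to 5.1% false positives;
- smallest p-value among three models (unadjusted; NAS; NAS plus TBSA): 7.1% to 9.2%;
- smallest p-value over all subsets of four covariates (NAS, TBSA, age, gender): 8.6% to 11.7%.

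**5. If baseline were session-specific.** Suppose earlier doses lower each later pre-dose rating by c points. Session 1 is unaffected and the other 10 of 11 lose c, so a raw change score averages 2.0 − c × 10/11:

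- c = 0.5: 2.0 − 0.455 = 1.55 points;
- c = 1.0: 2.0 − 0.909 = 1.09 points.

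By the normal approximation with SD unchanged, power at 47 per arm falls from 81% to 59% and 34%. An ANCOVA with slope b on that rating loses only b times as much. With b = 0.5 (assumed) it would show 2.0 − 0.227 = 1.77 or 2.0 − 0.455 = 1.55 points.

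**The case against.** The strongest reply is that the plan already does most of what is asked. It selects ANCOVA partly for its power and its ability to adjust for baseline. Its association rule brings in prognostic variables even when the arms are balanced, with TBSA as a named example. Applied mechanically, the two rules together match fixed adjustment to within 0-2 points of power, with type I error near 5%. This stands. The 84-94% figures therefore measure the gain over an unadjusted analysis, not over the plan as written.

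A reader might infer that the triggered rules bias the treatment estimate. The simulations do not support that; the largest bias was about 0.04 NAS points.

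A reader might also infer that the primary change score uses each session's own pre-dose rating. The documents do not say so. The change-score sentence belongs to time to maximal relief. Within a session any baseline is a constant, so the time of the lowest rating does not depend on it. The sample size is built on mean pain, not on change. What stands is that baseline is undefined for the primary analysis and the session-specific reading is open.

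The reply does not answer the discretion point. A mechanical rule needs thresholds, and the plan has none.

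**Conclusion.** The concern holds as one of pre-specification. The covariate set is left to the data, and ANCOVA's baseline term is neither fixed nor defined. The main consequence is that a false-positive rate of about 7-9% becomes possible under favourable choice among three plausible models. That is what the wording allows, not a prediction of how the analysts would behave.

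The power consequence depends on the comparator: about 4 to 14 points at 47 per arm over no adjustment (80% to 84-94%), nearly as much over the imbalance rule alone, and 0-2 points over both rules applied mechanically. These figures rest on assumed correlations. Entry requires an emergency-room or admission NAS of at least 5, which may narrow the range of baseline scores, so the lower correlations should not be dismissed.

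Loss of effect through a session-specific baseline is conditional twice over: on that reading being adopted, and on carryover of a size the documents do not give.

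**What to change.** In the Data Analysis Plan, before unblinding:

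1. State that the primary pain model includes treatment arm, the NAS taken before the first study dose, and TBSA, whatever the observed balance or association.
2. Define baseline for the primary pain analysis as that pre-first-dose NAS, for every session. Two ratings could qualify: the one just before study drug at session 1 and the one at the first examination. The text should name one.
3. Confine imbalance- and association-triggered adjustment, including the completion review described after Randomization, to sensitivity analyses labelled as such.

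The cost is wording only. Both variables are already among the baseline data to be recorded, and neither the sample size nor trial conduct changes.
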